9.1.1.1 Replacement policy

Patients failing the screening visit (detectable levels of SARS-CoV-2 serum functional antibodies) will be replaced. Patients successfully screened who do not receive a mod-RNA SARS-CoV-2 vaccination according to EU SmPC within 1 month after screening will be excluded from the study and replaced unless the patient is currently not eligible for SARS-CoV-2 vaccination by local regulation. In this case, the Novartis Medical Advisor should be contacted to discuss further proceeding including re-evaluation of anti-SARS-CoV-2 antibody level and PCR test. Patients developing symptoms of COVID-19 or have a SARS-CoV-2 infection (positive test result) between screening and first vaccination will be excluded from the study and will be replaced.

9.1.2 Withdrawal of informed consent

Participants may voluntarily withdraw consent to participate in the study for any reason at any time. Withdrawal of consent occurs only when a participant:

- Does not want to participate in the study anymore,
and
- Does not want any further visits or assessments
and
- Does not want any further study related contacts

In this situation, the investigator should make a reasonable effort (e.g. telephone, e-mail, letter) to understand the primary reason for the participant's decision to withdraw his/her consent and record this information.

Where consent to the use of personal and coded data is not required, participant therefore cannot withdraw consent. They still retain the right to object to the further use of personal data.

Study treatment must be discontinued and no further assessments conducted, and the data that would have been collected at subsequent visits will be considered missing.

Further attempts to contact the participant are not allowed unless safety findings require communicating or follow-up.

All efforts should be made to complete the assessments prior to study discontinuation. A final evaluation at the time of the participant's study discontinuation should be made as detailed in the assessment table.

Novartis will continue to retain and use all research results (data) that have already been collected for the study evaluation.

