6.2.1.1 Permitted concomitant therapy requiring caution and/or action

a) For cohort 1 and 2:

Antineoplastic, immune-modulating or immunosuppressive therapies

Siponimod has not been studied in combination with antineoplastic, immune-modulating or immunosuppressive therapies. Caution should be exercised during concomitant administration due to the risk of additive immune effects during such therapy and in the weeks after administration of any of these medicinal products.

Due to the characteristics and duration of alemtuzumab immune suppressive effects described in its product information, initiating treatment with siponimod after alemtuzumab is not recommended unless the benefits of treatment clearly outweigh the risks for the individual patient.

Anti-arrhythmic medicinal products, QT-prolonging medicinal products, medicinal products that may decrease heart rate

During treatment initiation siponimod should not be concomitantly used in patients receiving class Ia (e.g. quinidine, procainamide) or class III (e.g. amiodarone, sotalol) anti-arrhythmic medicinal products, QT-prolonging medicinal products with known arrhythmogenic properties, heart-rate-lowering calcium channel blockers (such as verapamil or diltiazem) or other substances that may decrease heart rate (e.g. ivabradine or digoxin) because of the potential additive effects on heart rate (see section 4.4 of Siponimod SmPC). No data are available for concomitant use of these medicinal products with siponimod. Concomitant use of these substances during treatment initiation may be associated with severe bradycardia and heart block. Because of the potential additive effect on heart rate, treatment with siponimod should generally not be initiated in patients who are concurrently treated with these substances (see section 4.4 of Siponimod SmPC). If treatment with siponimod is considered, advice from a cardiologist should be sought regarding the switch to non-heart-rate-lowering medicinal products or appropriate monitoring for treatment initiation.

Beta blockers

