9.1 Discontinuation and completion

9.1.1 Study treatment discontinuation and study discontinuation

All medication is part of clinical routine.

Discontinuation of study treatment for a participant occurs when study treatment is stopped earlier than the protocol planned duration and can be initiated by either the participant or the investigator.

The investigator must discontinue study treatment for a given participant if, he/she believes that continuation would negatively impact the participant's well-being.

Study treatment must be discontinued under the following circumstances:

- Participant/guardian decision
- Pregnancy
- Use of prohibited treatment as per recommendations in the prohibited treatment section
- New medical condition not allowing for continuation of study treatment
- Any situation in which study participation might result in a safety risk to the participant
- Adverse events, abnormal laboratory values or abnormal test result that indicate a safety risk to the participant.

Study discontinuation of a participants occurs under the following circumstances:

- Significant non-compliance
- Retroactive failure to fulfil inclusion/exclusion criteria
- Enrolment in any other clinical trial involving an investigational product or enrolment in any other type of medical research judged not to be scientifically or medically compatible with this study

Participants who decide they do not wish to participate in the study further should NOT be considered withdrawn from the study UNLESS they withdraw their consent (see Section 9.1.2 'Withdrawal of Informed Consent' section). **Where possible, they should return for the assessments indicated** in the Assessment Schedule. If they fail to return for these assessments for unknown reasons, every effort (e.g. telephone, e-mail, letter) should be made to contact the participant/pre-designated contact as specified in the lost to follow-up section. This contact should preferably be done according to the study visit schedule.

Patients completing the vaccination cycle but do not come to the center for the blood draw one week later (6-10 days after second vaccination) will be excluded from the study.

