9.2 Study completion and post-study treatment

Study completion is defined as when the last participant finishes their Study Completion visit and any repeat assessments associated with this visit have been documented and followed-up appropriately by the Investigator or, in the event of an early study termination decision, the date of that decision.

All patients in the present study are treated as part of the clinical routine. The interventional character of the study is limited to collection and analysis of blood samples.

There is no plan for further treatment and medical care for the study participants after the end of the clinical trial. After completion, all study participants regardless of the reasons will continue to be cared for as part of the clinical routine and further treatment will be discussed individually with investigator.

10 Safety monitoring and reporting

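### Protocol 9.1.2 orders study treatment stopped when consent is withdrawn, although study treatment is the patient's routine MS drug and vaccine, which the trial says it does not touch; a minor wording correction

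*Protocol*

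**What the plan says.** Protocol 9.1.2 defines withdrawal of consent by three conditions that must all hold: the participant no longer wants to take part, wants no more visits or assessments, and wants no more study-related contact. None of the three concerns the MS drug or the vaccine. The section then gives the rule "Study treatment must be discontinued and no further assessments conducted", and the same sentence goes on to treat data from later visits as missing.

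The documents are consistent about what study treatment is. The protocol summary lists siponimod and the first-line drugs under that label. Table 6-1 lists them with the vaccines. Section 8.1 classes both MS drugs and vaccinations as investigational products. SAP 2.1.1 defines both as study treatments.

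They are equally consistent about what the trial does. Section 4.2 leaves continuing or interrupting siponimod to physician and patient, independently of the study. Sections 4.5 and 6.1 state that individual treatment is not interfered with. Section 6.1.2 says there is no supply. Section 9.2 adds: "The interventional character of the study is limited to collection and analysis of blood samples".

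**The concern.** A participant can leave a blood-sampling study without any reason to change therapy. As written, 9.1.2 makes leaving the study a mandatory reason to stop it. For a cohort 1 patient this means stopping siponimod. For a cohort 2 patient in the middle of the break it means not restarting. For a cohort 3 patient on a first-line drug it means stopping that drug. For anyone between doses it means forgoing the second vaccination.

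The protocol itself shows why this is the wrong direction for an error. Section 1.1 repeats the product label's caution that disease activity may return when siponimod is stopped for vaccination. Section 4.1 argues against randomisation because it would override the decision that physician and patient make from the individual MS history. A literal 9.1.2 would override that same decision for an administrative reason. At stake are the consistency of the protocol and, in principle, a patient's continued therapy. The trial's estimates are not at stake.

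**Working it through.** The plan states no figure on this point, so the check sets the texts side by side.

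1. **The order.** Section 9.1.2 is triggered by withdrawal of consent alone. It carries no condition and no exception for routine medication.
2. **Its object.** The protocol summary, Table 6-1, section 8.1 and SAP 2.1.1 all make the MS drug, the vaccine or both study treatment. I found no narrower definition under which the order would apply only to study procedures.
3. **The opposing statements.** Sections 4.2, 4.5, 6.1 and 9.2 say the trial does not steer these treatments and that its intervention is blood sampling. Section 3 says the same about the interventional part. An order to stop a drug that the trial neither supplies nor controls cannot be squared with them.
4. **Is there a passage that cures it?**
   - Section 9.1.1 opens with "All medication is part of clinical routine". This says where the drug comes from. It does not limit the later order in 9.1.2.
   - Section 9.2 says that "all study participants regardless of the reasons will continue to be cared for as part of the clinical routine". That is helpful, but the sentence is tied to the time after completion and does not name withdrawal of consent.
   - Section 6.1.2 (no supply) shows that the sponsor has nothing to take away. It does not remove the instruction to the investigator.
5. **Effect on the primary endpoint.** The treatment order could reach it only through a withdrawal between dose 1 and dose 2 that led to dose 2 being withheld. Protocol 12.3.3 would then count the patient as a non-responder. The SAP footnote to the efficacy analysis set (printed under SAP 2.3.1) says all patients received the second dose, so this did not happen. A withdrawal after dose 2 but before the week 1 sample would remove the patient from the analysis. The cause would be the end of sampling, which is proper, and not the treatment order.
6. **Effect on later endpoints.** Study assessments end on withdrawal, so stopping the drug from that moment could not alter a later antibody or T-cell measurement in the study.
7. **Effect on planned figures.** The 20 participants per arm, the 22 to be enrolled, and the margins of error of 20.1%, 19% and 17.5% in section 12.6.1 do not depend on the sentence. The Clopper-Pearson method is likewise untouched.

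**The case against.** The strongest defence is that no sensible investigator would act on the sentence. The same chapter opens by placing all medication in clinical routine, the sponsor supplies nothing, and the reference in 9.2 to any reason makes most sense if it also covers people who leave early. SAP 2.1.1 adds a possible reading: MS treatment becomes study treatment at informed consent, so withdrawing consent might end that status while the prescription continues. The caution about disease activity also concerns stopping siponimod for vaccination, so applying it to a stop at withdrawal is an inference. It says nothing about untreated patients in cohort 3.

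Much of this stands. It makes the intent clear and the practical risk low. It does not repair the rule. Neither document states that study-treatment status lapses with consent, and the other passages have to be read against the plain words of 9.1.2 rather than with them.

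Two stronger readings are tempting, and the documents do not support them.

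- A reader might infer that section 9.1.1 has the same defect, because it has a list headed "Study treatment must be discontinued under the following circumstances" that begins with "Participant/guardian decision". But 9.1.1 first defines treatment discontinuation as an early stop of the treatment, begun by participant or investigator. It lists study discontinuation separately and deals in a further paragraph with participants who do not wish to continue. In that structure the bullet naturally means a decision to stop the drug. Pregnancy, a new medical condition and safety risk could equally lead to a stop in routine care.
- A reader might also make something of the bullet "Use of prohibited treatment as per recommendations in the prohibited treatment section", since the only subsection under 6.2.1 is titled "Permitted concomitant therapy requiring caution and/or action". This is a clerical cross-reference with no bearing on withdrawal of consent. Section 6.2.1.1 does contain a prohibition, on live vaccines during siponimod and for 4 weeks afterwards, so a missing section title does not show that the bullet is empty.

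**Conclusion.** The point holds for the one sentence in 9.1.2. It is wrong as written and contradicts 4.2, 4.5, 6.1 and 9.2. That it is leftover template wording is an inference, though a likely one. That the practical risk is low is a judgement, resting on the absence of drug supply and on the consistent references to routine care.

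The size is small: one clause, no planned figure changed and no analysis affected. A reader might infer that the primary result was put at risk; the SAP footnote on second doses rules out the only route. A reader might also take the 10% drop-out allowance in 12.6.1 as the number of patients exposed to the rule. It is a planning allowance for sample size and does not count consent withdrawals, for which the documents give no figure.

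The benefit to current participants may also be limited. Amendment 2 ends recruitment, and the SAP history records an update after final data review. This is a consistency correction worth making, at the minor end.

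**What to change.** In protocol 9.1.2, replace the clause that orders treatment stopped with: *On withdrawal of consent, study-specific blood sampling, assessments and contacts stop; MS treatment and any outstanding vaccine dose remain a decision of the treating physician and patient in clinical routine.* Keep the remainder of the sentence, on treating later data as missing. Section 9.1.1 needs no change for this point.

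The cost is one wording edit, with no new procedures, data or analyses and no change to the SAP. Section 14.1 requires a written amendment with the usual approvals, so the edit should be bundled with the next amendment made for another reason.

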9.1.3 Lost to follow-up

For participants whose status is unclear because they fail to appear for study visits without stating an intention to discontinue or withdraw, the investigator must show "due diligence" by documenting in the source documents steps taken to contact the participant, e.g. dates of telephone calls, registered letters, etc. A participant should not be considered as lost to follow-up until due diligence has been completed.

9.1.4 Early study termination by the sponsor

The study can be terminated by Novartis at any time.

Reasons for early termination:

- Unexpected, significant, or unacceptable safety risk to participants enrolled in the study
- Decision based on recommendations from applicable board(s) after review of safety and efficacy data

In taking the decision to terminate, Novartis will always consider participant welfare and safety. Should early termination be necessary, participants must be seen as soon as possible and treated as a prematurely withdrawn participant. The investigator may be informed of additional

procedures to be followed in order to ensure that adequate consideration is given to the protection of the participant's interests. The investigator or sponsor depending on local regulation will be responsible for informing IRBs/IECs of the early termination of the trial.

9.2 Study completion and post-study treatment

Study completion is defined as when the last participant finishes their Study Completion visit and any repeat assessments associated with this visit have been documented and followed-up appropriately by the Investigator or, in the event of an early study termination decision, the date of that decision.

All patients in the present study are treated as part of the clinical routine. The interventional character of the study is limited to collection and analysis of blood samples.

There is no plan for further treatment and medical care for the study participants after the end of the clinical trial. After completion, all study participants regardless of the reasons will continue to be cared for as part of the clinical routine and further treatment will be discussed individually with investigator.

10 Safety monitoring and reporting

10.1 Definition of adverse events and reporting requirements

10.1.1 Adverse events

An adverse event (AE) is any untoward medical occurrence (e.g. any unfavorable and unintended sign [including abnormal laboratory findings], symptom or disease) in a clinical investigation participant after providing written informed consent for participation in the study. Therefore, an AE may or may not be temporally or causally associated with the use of a medicinal (investigational) product.

The investigator has the responsibility for managing the safety of individual participant and identifying adverse events.

Novartis qualified medical personnel will be readily available to advise on trial related medical questions or problems.

The occurrence of adverse events must be sought by non-directive questioning of the participant at each visit during the study. Adverse events also may be detected when they are volunteered by the participant during or between visits or through physical examination findings, laboratory test findings, or other assessments.

Adverse events must be recorded under the signs, symptoms, or diagnosis associated with them, accompanied by the following information (as far as possible) (if the event is serious refer to Section 10.1.2):

1. The Common Toxicity Criteria (CTC) AE grade (version 5 or higher):

Adverse events will be assessed and graded according to the Common Terminology Criteria for Adverse Events (CTCAE) version. CTCAE grade 5 will be used to capture death information within the eCRF.

2. Its relationship to the study treatment. If the event is due to lack of efficacy or progression of underlying illness (i.e. progression of the study indication) the assessment of causality will usually be 'Not suspected.' The rationale for this guidance is that the symptoms of a lack of efficacy or progression of underlying illness are not caused by the trial drug, they happen in spite of its administration and/or both lack of efficacy and progression of underlying disease can only be evaluated meaningfully by an analysis of cohorts, not on a single participant
3. Its duration (start and end dates) or if the event is ongoing, an outcome of not recovered/not resolved must be reported
4. Whether it constitutes a SAE (see Section 10.1.2 for definition of SAE) and which seriousness criteria have been met
5. Action taken regarding with study treatment.

All adverse events must be treated appropriately. Treatment may include one or more of the following:

- Dose not changed
 - Dose Reduced/increased
 - Drug interrupted/withdrawn
6. Its outcome (i.e. recovery status or whether it was fatal)

Conditions that were already present at the time of informed consent should be recorded in medical history of the participant.

Adverse events (including lab abnormalities that constitute AEs) should be described using a diagnosis whenever possible, rather than individual underlying signs and symptoms.

Adverse event monitoring should be continued for at least 30 days following the last study visit (Covid-19 follow-up call).

Once an adverse event is detected, it must be followed until its resolution or until it is judged to be permanent (e.g. continuing at the end of the study), and assessment must be made at each visit (or more frequently, if necessary) of any changes in severity, the suspected relationship to the interventions required to treat it, and the outcome.

Information about adverse drug reactions for the investigational drug can be found in the Investigator's Brochure (IB).

Abnormal laboratory values or test results constitute adverse events only if they fulfill at least one of the following criteria:

- they induce clinical signs or symptoms
- they are considered clinically significant
- they require therapy

Clinically significant abnormal laboratory values or test results must be identified through a review of values outside of normal ranges/clinically notable ranges, significant changes from baseline or the previous visit, or values which are considered to be non-typical in participant with the underlying disease.

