- *Vaccinations may be less effective if administered during siponimod treatment. Discontinuation of treatment 1 week prior to planned vaccination until 4 weeks after is recommended. When stopping siponimod therapy for vaccination, the possible return of disease activity should be considered*

The modRNA vaccine BNT162b2 was shown to not only trigger a vaccine-induced antibody response against the receptor binding domain (RBD) of the SARS-CoV-2 spike protein but also a functional and proinflammatory CD4+ and CD8+ T-cell response in a phase I/II trial (NCT04380701) (Sahin et al, 2020). In the following phase III trial with 43,548 participants (NCT04368728), BNT162b2 mRNA vaccine has further been shown to be 95% effective in

preventing COVID-19 (Polack et al, 2020). Similar results were also shown for the mRNA vaccine developed by Moderna: the efficacy of mRNA-1273 in preventing COVID-19 in a phase III trial with 30,420 participants was 94.1% (NCT04470427) (Lindsay et al, 2021).

It is therefore essential to understand the immune response to the novel class of modRNA vaccines in siponimod treated patients where S1P1 expressing Th17 cells are retained in lymph nodes (Behrangi et al, 2019) to develop a guidance for SARS-CoV-2 vaccination strategies in the vulnerable population of SPMS patients. This becomes even more important when considering that SARS-CoV-2 vaccination needs to be boosted after 3 or 4 weeks, resulting in a possible treatment interruption of about 2-3 months.

The detection of SARS-CoV-2 serum functional antibodies after vaccination in patients negative for this parameter at baseline is defined as seroconversion according to World Health Organization guidelines (WHO guideline, 2020). In this study, we will test for functional antibodies, i.e. antibodies that inhibit the binding of the viral spike protein to the human angiotensin-converting enzyme 2 (ACE2) receptor, which is the first and necessarily required step during SARS-CoV-2 infection (Yang et al, 2020). Vaccination response will be analyzed during continued siponimod treatment (cohort 1) or a short treatment interruption (cohort 2) in accordance with label recommendations / upon discretion of the treating physician to cover both scenarios taking place in clinical practice.

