
 Describing SARS-CoV-2 serum functional antibody levels in participants treated concomitantly with siponimod versus siponimod treatment break versus first-line DMTs and in patients currently not on a DMT Describing the T-cell response to modRNA vaccines in participants treated concomitantly with siponimod versus siponimod treatment break versus first-line DMTs and in patients currently not on a DMT Describing safety, incl. AEs related to discontinuation and new onset of siponimod treatment and patients developing COVID-19 	
 SARS-CoV-2 serum functional antibody levels one week, one month and six months after second dose of vaccine and additionally one month after an optional booster vaccination in participants treated concomitantly with siponimod versus siponimod treatment break versus first-line DMTs and in patients currently not on a DMT SARS-CoV-2 specific T-cell levels one week, one month and six months after second dose of vaccine and additionally one month after an optional booster vaccination in participants treated concomitantly with siponimod versus siponimod treatment break versus first-line DMTs and in patients currently not on a DMT measured by e.g. enzyme-linked immunosorbent spot (ELIspot) assay from peripheral blood mononuclear cells that were stimulated with SARS-CoV-2 peptide mix AEs, SAEs, incl. patients with clinical confirmed COVID-19, events leading to discontinuation in participants treated concomitantly with siponimod versus siponimod treatment break versus first-line DMTs and in patients currently not on a DMT

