4.5 Risks and benefits

This study does not interfere with clinical routine treatment of MS patients regarding DMTs or SARS-CoV2 vaccinations. The only intervention is the blood sampling at specific time-points in the course of this trial. In the case that a blood sampling for antibody and T-cell response measurement is not related to a clinical routine blood draw, during patient's regular consultation, this blood draw could bear some minimal risk for the patient, associated with the sampling procedure (venous puncture). As of February 2021, for the currently EU approved mRNA vaccines (*COMIRNATY®* by BioNTech/Pfizer, *COVID 19 Vaccine Moderna* by Moderna), no data on safety and efficacy are available for patients with immunomodulating/immunosuppressive treatment as this condition was excluded from pivotal phase III clinical trials. However, as vaccines based on nucleoside modified RNA do not contain living viral particles, the risk to experience adverse events is considered similar as for healthy individuals. Thus, the risk evaluation for patients with immunomodulatory/immunosuppressive treatment is the same as for any other individual and the risks of the vaccine are considered much lower than the risks of suffering from (a severe course of) COVID-19 in the future.

However, this study involves the risk to reveal a reduced or insufficient immune response after vaccination in patients with immunomodulatory/immunosuppressive treatment. Although no data and recommendations are available for these circumstances, such a situation might require additional booster vaccination. Furthermore, the vaccine itself might have an effect on MS disease activity or on the anti-MS effect of the concomitant

immunosuppressing/immunomodulating therapy. However, no increased disease activity has been reported in MS patients in Israel that have received SARS-CoV-2 mRNA vaccination (DMSG statement, February 2021).

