#### **2.1.1 General definitions**

##### **Study treatments**

The modRNA vaccine and the treatment for MS are defined both as study treatments. More specifically, the MS treatment is established as study treatment from the time of informed consent.

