### **2.8.1 Adverse events (AEs)**

According to the CSP all adverse events starting in the on-treatment period, i. e. the treatment emergent AEs, are analyzed.

The on-treatment period lasts from the date of first administration of study treatment after informed consent to 30 days after the month 12 COVID-19 follow-up call.

The number (and percentage) of subjects with treatment-emergent adverse events will be summarized in the following ways:

- by treatment group (cohort 1-3), primary system organ class and preferred term.
- by treatment group (cohort 1-3), primary system organ class, preferred term and maximum severity

A subject with multiple AEs within a MedDRA primary system organ class is only counted once towards the total of the primary system organ class.

A subject with multiple AEs within a preferred term is only counted once towards the total of the preferred term class.

Separate summaries will be provided for study medication related AEs, death, SAEs, AEs leading to discontinuation and adverse events leading to dose adjustment.

The absolute and relative frequency of COVID-19 infections is presented.

Deaths and serious adverse events are listed in addition.

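### No planned output can tie adverse events or MS activity to the siponimod break, its restart or a vaccine dose, although the safety objective asks for this

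*Protocol*

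**What the plan says.** The secondary safety objective (Protocol section 2, Table 2-1; repeated in SAP 1.2) is worded causally: "Describing safety, incl. AEs related to discontinuation and new onset of siponimod treatment and patients developing COVID-19". The endpoint paired with it is not. It is adverse events and serious adverse events by cohort, including confirmed COVID-19 and events leading to discontinuation.

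Protocol 10.1.1 asks the investigator for each event's relationship to the study treatment. It adds guidance that for an event due to "lack of efficacy or progression of underlying illness (i.e. progression of the study indication) the assessment of causality will usually be 'Not suspected". Two reasons are given, joined by and/or: the symptoms are not caused by the drug because "they happen in spite of its administration", and such outcomes "can only be evaluated meaningfully by an analysis of cohorts, not on a single participant".

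Two products are under study. SAP 2.1.1 states: "The modRNA vaccine and the treatment for MS are defined both as study treatments". The protocol recognises two ways in which MS activity might be affected. Section 1.1 cites the label: "When stopping siponimod therapy for vaccination, the possible return of disease activity should be considered". Section 4.5 says that "the vaccine itself might have an effect on MS disease activity".

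On outputs, SAP 2.8.1 tabulates all treatment-emergent events by cohort and then says: "Separate summaries will be provided for study medication related AEs", alongside deaths, serious events, and events leading to discontinuation or dose adjustment. SAP 2.7.1 measures MS activity by relapses and presents a crude annual relapse rate to end of study, with the relapse count and patient-years.

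**The concern.** An objective about events related to discontinuation and new onset needs either a causality judgement against the break and the restart, or a tabulation by when events occurred relative to them. The plan has neither.

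The causality route is weak for MS events. The usual code is Not suspected, and one of its two reasons assumes the drug is being taken. In cohort 2 siponimod is paused for about 2 to 3 months, and under Amendment 2 patients in cohorts 1 and 2 may also pause for a booster. The related table does not separate vaccine from MS drug, and the text gives no place for relatedness to the interruption.

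The timing route is absent: the relapse rate runs over the whole of follow-up. At stake is whether the report can say anything specific about disease activity after a pause or a dose, which bears on the benefit-risk question that physicians and patients face.

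**Working it through.** The documents give no event count or causality share, so the main check is a trace from the objective to the planned outputs. The arithmetic that follows is illustration on stated assumptions.

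**Step 1. What each planned output can show**

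| Output | Filtered on causality? | Split by vaccine / MS drug / interruption? | Split by break, restart or dose? |
|---|---|---|---|
| All treatment-emergent events by cohort (Protocol 12.4.1, SAP 2.8.1) | No | No | No |
| Serious events (same sections) | No | No | No |
| Events leading to discontinuation or dose adjustment (same sections) | No | No | No; these are events that cause a stop, not events that follow one |
| Study-medication-related events (same sections) | Yes | No | No |
| Crude annual relapse rate (SAP 2.7.1) | No | Not applicable | No; pooled to end of study |
| Duration of the cohort 2 interruption (SAP 2.4.1) | Not applicable | Not applicable | Describes exposure, not events |

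No row has an entry that answers the objective. Worsening without relapse can appear only as an adverse event; it has no analysis of its own.

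**Step 2. Does the reason for the default hold?**
- Event during a siponimod pause: the drug is not being given, so the first reason does not apply.
- Event after a vaccine dose: the vaccine is also a study treatment and section 4.5 raises an effect on MS activity, so it cannot be presumed that the event happened despite treatment.
- The second reason, evaluation by cohort, is not affected by either. Its support here is limited. Cohort membership follows the individual MS history (Protocol 4.1), no formal cohort comparison is planned (Protocol 2.1), and the relapse rate is not timed to the break.

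**Step 3. What the related table would show**
Assume k patients in a cohort of 20 have an MS event, and each is coded as suspected with probability s. The expected number in the related table is k × s, and the chance that it shows none is (1 − s)^k.
- s = 0: expected 0; chance of none 100%.
- k = 2, s = 0.25: expected 0.5; chance of none 0.75² = 56%.
- k = 4, s = 0.25: expected 1.0; chance of none 0.75⁴ = 32%.

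The all-causality table shows all k in each case, if they are reported as adverse events starting in the on-treatment period. As an extreme, 3 of 20 is 15% (exact 95% CI 3.2 to 37.9%), while a related table with the default always applied shows 0 of 20 (upper limit 1 − 0.025^(1/20) = 16.8%).

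**Step 4. How far pooling dilutes the relapse rate**
Take 2 to 3 months as 8.67 to 13 weeks, and follow-up as the stated 56 to 60 weeks. SAP 2.7.1 does not say where patient-years start, so this denominator is an assumption. The break is then f = 8.67/60 = 14% to 13/56 = 23% of follow-up. If the relapse rate is multiplied by m during the break only, the pooled rate is multiplied by 1 + f(m − 1).
- m = 2: 1.14 to 1.23.
- m = 4: 1.43 to 1.70.

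A doubling confined to the break would therefore appear as a rise of 14 to 23% in a crude rate from about 20 patients.

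One point to confirm: the relapse row of Table 8-1 appears unmarked at the month-12 call, although the rate runs to end of study. The table may have been damaged in extraction.

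**The case against.** A reader might infer that investigators are told to code relapses as unrelated, so that MS activity vanishes from the safety results. The documents do not support this.
- The guidance is conditional and says usually. It does not name relapse, and an event the investigator attributes to the vaccine or to stopping siponimod need not fall under it.
- The endpoint paired with the objective has no causality filter. All treatment-emergent events and serious events are tabulated by cohort whatever the code.
- Relapse has its own row in the assessment schedule and its own rate in SAP 2.7.1, neither of which depends on causality.
- The cohort-level reason for the default is separate from the one that fails, so the rationale as a whole is not refuted.

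A reader might also infer that expedited reporting is broadly compromised. Protocol 10.1.3 sends every serious event to the sponsor within 24 hours regardless of causality. Suspected causality matters only at the later steps, namely SUSAR assessment and serious events after study completion. Return of disease activity on stopping is already in the label text the protocol quotes, which bears on whether such an event would be unexpected.

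Finally, the eCRF is not among the documents and may record causality per product.

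All of this stands, and it limits the harm. It does not supply an output by source or by time window.

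**Conclusion.** The point holds as a gap between the objective and the outputs, and it should be fixed. Nothing planned attributes adverse events or MS activity to the break, the restart or a vaccine dose. The one causality-based table is undivided and is likely to under-count MS events, because the usual code rests partly on a premise that does not fit a pause or a vaccine effect.

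The loss is confined to that table and to the absence of timing; MS events recorded as adverse events, and relapses, remain visible elsewhere. The size cannot be computed from the documents. The figures of 0 to 1 shown out of 2 to 4, and a 14 to 23% pooled rise for a doubling during the break, rest on assumed event counts, coding shares and follow-up. The 3 of 20 against 0 of 20 contrast assumes that the default is always applied, which the text does not say.

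**What to change.** 1. In SAP 2.7.1 and 2.8.1, add a table of all MS relapse and worsening events by cohort, whatever the causality code, split by window: during a siponimod break, after restart, and after each vaccine dose including a booster. Give patients, events and patient-time per window, and state how overlapping windows are handled. Vaccination dates are documented under Protocol 8.1, and the interruption dates are needed already for the duration in SAP 2.4.1. Dates of booster-related breaks should be confirmed from the MS medication record.
2. Where the eCRF records it, split the related-event table into vaccine-related and related to the MS drug or its interruption. If it does not, say so in the report.
3. State in Protocol 10.1.1 and in the report that the Not suspected default should not be applied automatically to MS events starting during or after a break or after a vaccine dose, and that the related-event table may under-count them.

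Do not rely on recoding causality in retrospect. The study is open-label and the SAP was last revised after final data review, so recoding could itself introduce bias.

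The cost is a few more descriptive tables with small counts and wide intervals, and a paragraph of explanation. No new data collection is needed if the dates are complete.
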